7.2. Efficacy Endpoints

The efficacy evaluation criteria described in Section 7.1 will be used to derive the following primary and secondary efficacy endpoints (Table 9). Definitions of each endpoint are provided in Section Section 10.5.2.

Table 9: Efficacy Endpoints

Primary	Secondary
ORR (Cohorts 1 and 2)	CR rate (Cohort 3); ORR (Cohort 4)
CBR (Cohort 3)	DOR (All)
6-month PFS (Cohort 4)	CBR (Cohorts 1, 2, and 4)
	PFS (All)
	6-month PFS (Cohorts 1, 2, and 3)
	OS (All)

Abbreviations: CBR=clinical benefit rate; DOR=duration of response; ORR=objective response rate; OS=overall survival; PFS=progression-free survival

7.2.1. Response Criteria

Efficacy evaluation will include the assessment of target and non-target tumor responses as well as objective responses. Responses will be assessed as defined in the statistical analysis plan (SAP).

7.2.1.1. Target and Non-Target Response Assessments

Assessments will be based on the definitions for target and non-target lesions described in Table 10.

Table 10: Target and Non-target Lesions

TARGET LESIONS		
Lesions Response:	Definition:	
Complete Response (CR)	Disappearance of all target lesions. Any pathological lymph node must have	
	reduction in short axis to <10 mm	
Partial Response (PR)	At least a 30% decrease in the sum of diameters of the target lesions, taking as a reference the baseline sum diameters	
Progressive Disease (PD)	At least a 20% increase in the sum of diameters of the target lesions, taking as	
	a reference the smallest sum on study, including the baseline sum. In addition	
	to the relative increase of 20%, the sum must also demonstrate an absolute	
	increase of at least 5 mm. Definitive new lesion presence also indicates	
	progression.	
Stable Disease (SD)	Neither sufficient shrinkage to qualify for PR nor sufficient increase to qualify	
	for PD, referencing the smallest sum diameters while on study.	
NON-TARGET LESIONS		
Lesions Response:	Definition:	
Complete Response (CR)	Disappearance of all non-target lesions and normalization of tumor marker	
	level. All lymph nodes must be non-pathological in size (<10-mm short axis)	
Partial Response (PR)	Persistence of one or more non-target lesion(s) and/or maintenance of tumor	
	marker level above the normal limits	
Progressive Disease (PD)	Unequivocal progression of existing non-target lesions (see following	
	definition).	

Abbreviations: CR=complete response; PD=progressive disease; PR=partial response; SD=stable disease

Progression in Non-target Disease: There must be an overall level of substantial worsening in non-target disease such that, even in the presence of SD or PR in target disease, the overall tumor burden has increased sufficiently to merit discontinuation of therapy.

7.2.1.1.1. Additional Criteria to Consider When Making Tumor Response Assessments

Because worsening in non-target disease cannot be easily quantified, a useful test that can be applied when assessing patients for unequivocal progression is to consider if the increase in overall disease burden based on the change in non-measurable disease is comparable in magnitude to the increase that would be required to declare PD for measurable disease (ie, an increase in tumor burden representing an additional 73% increase in "volume" [which is equivalent to a 20% increase in the diameter of a measurable lesion]).

When effusions are known to be a potential adverse effect of treatment, cytological confirmation of the neoplastic origin of any effusion that appears or worsens during treatment when the measurable tumor has met criteria for response or SD is not mandatory, but might be performed to differentiate between response (or SD) and PD when substantial change of effusion and or ascites is noted.

If a patient is discontinued from the study before PD occurs and receives local or regional palliative radiotherapy during the follow-up period, the irradiation site must be omitted from the response assessment of the patient; however, if the site is observed to demonstrate disease progression, this case should be judged as PD.

For equivocal findings of progression (eg, very small and uncertain new lesions; cystic changes or necrosis in existing lesions), treatment may continue until the next scheduled assessment. If at the next scheduled assessment, progression is confirmed, the date of progression should be the earlier date when progression was suspected.

7.2.1.2. Objective Response Assessment

Assessments will be based on the definitions provided in Table 11 and Table 12.

Since this is a non-randomized study, all responses (CR/PR) must be confirmed.

Table 11: Time Point Response for Patients with Target (±Non-target) Disease

Target	Non-Target	New	Objective
Lesions	Lesions	Lesions	Response
CR	CR	No	CR
CR	Non-CR/Non-PD or Not all evaluated	No	PR
PR	Non-PD or Not all evaluated	No	PR
SD	Non-PD or Not all evaluated	No	SD
Not all evaluated	Non-PD	No	NE
PD	Any	Yes or No	PD
Any	PD	Yes or No	PD
Any	Any	Yes	PD

Abbreviations: CR=complete response; NE=not evaluable; PD=progressive disease; PR=partial response; SD=stable disease

Table 12: Time Point Response for Patients with Only Non-target Disease

Non-Target Lesions	New Lesions	Objective Response
CR	No	CR
Non-CR/Non-PD	No	SD
Not all evaluated	No	NE
Unequivocal PD	Yes or No	PD
Any	Yes	PD

Abbreviations: CR=complete response; NE=not evaluable; PD=progressive disease; PR=partial response; SD=stable disease

8. SAFETY INFORMATION

8.1. Adverse Events

8.1.1. Definitions of Adverse Events

An AE is any untoward medical occurrence in a clinical study patient and does not necessarily have a causal relationship with the study drug. An AE can therefore be any unfavorable and unintended sign (including an abnormal finding), symptom, or disease temporally associated with the use of a study drug, whether or not related to the study drug. This includes any occurrence that is new in onset or aggravated in severity or frequency from the baseline condition, or abnormal results of diagnostic procedures, including laboratory test abnormalities.

All AEs will be collected from the time the main ICF is signed through 30 days after the last dose of study therapy (safety follow-up) or until the start of new antitumor therapy, whichever is earlier. For AEs that occur between signing the pre-screening consent and main study ICF, there is no need to record those that are unrelated unless it is mandatory by local regulations. All AEs will be documented in the eCRF. Any untoward medical event that occurs after the safety follow-up is not considered an AE, unless the Investigator considers that the AE is related to the study drug. Serious AEs related to study therapy will be collected through the survival follow-up.

All AEs will be documented in the eCRF. Documentation should include onset and resolution/stabilization dates, severity/grade, relationship to study drug, and outcome of the event.

Signs and symptoms of a pre-existing disease should not be considered an AE, but should rather be considered baseline signs and symptoms. Worsening of pre-existing signs and symptoms is considered an AE.

For definitions and reporting of pregnancies, overdoses, and medication errors, refer to Section 8.5.1, Section 8.5.2, and Section 8.5.3, respectively.

8.1.2. Reporting of Adverse Events

8.1.2.1. Terms of Reported Adverse Events

All AEs will be documented in the eCRF according to the eCRF Completion Guidelines.

When a diagnosis for the reported signs or symptoms is known, the Investigator should report the diagnosis, not the symptoms, as the AE.

Adverse events can be spontaneously reported or elicited during open-ended questioning, examination, or evaluation of a patient in order to prevent reporting bias, patients should not be questioned regarding the specific occurrence of 1 or more AEs.

8.1.2.2. Severity of Adverse Events

The NCI-CTCAE Version 5.0 will be used to grade the severity of AEs.

8.1.2.3. Causal Relationship with Study Drug

The causal relationship between an AE and study drug will be assessed using the following 2-point scale, taking into account the patient's condition, medical history, concomitant medications, and the temporal relationship between study drug administration and onset of the event.

- 1. An AE is considered to be "Related" if the event follows a reasonable temporal sequence from administration of study drug and there is a **reasonable possibility** that at least one of the following conditions is true:
 - A positive dechallenge: This means that the event improves or resolves after the drug is stopped (temporarily or permanently).
 - A positive rechallenge: This means that the event reappears after the drug is restarted.
 - The event cannot be reasonably explained by the patient's clinical state and/or other therapies administered.
 - A single occurrence of an event that is uncommon and known to be strongly associated with drug exposure (eg, angioedema, Stevens-Johnson syndrome).
- 2. An AE is considered to be "Not related" if there is no reasonable possibility that:
 - The event occurred prior to study drug administration.
 - There is no reasonable possibility that the study drug caused the event.
 - The event does not follow a reasonable temporal sequence from administration of study drug and could have been produced by a documented pre-existing condition, concomitant medication or patient's clinical state.
 - For the purposes of safety reporting, "no reasonable possibility" means there is no evidence to suggest a causal relationship between the study drug and the AE.

8.1.2.4. Outcome of Adverse Events

Record the outcome of AEs as follows:

- 1. Resolved
- 2. Not resolved
- 3. Fatal

The AE reporting process is provided in the eCRF Completion Guidelines.

8.1.2.5. Follow-up of Adverse Events

Any ongoing AEs should be followed until the earliest occurrence of one of the following:

- The AE has resolved or stabilized
- Completion of Safety Follow-up visit
- Start of new antitumor therapy

- Withdrawal of consent
- Death
- Other (eg, transfer to another hospital)

8.2. Serious Adverse Events

8.2.1. Definitions of Serious Adverse Events

An SAE is any untoward medical occurrence that at any dose:

- Results in death
- Is life-threatening
 - The term "life-threatening" in the definition of "serious" refers to an event in which the patient was at risk of death at the time of the event; it does not refer to an event which hypothetically might have caused death if it were more severe.
- Requires inpatient hospitalization or prolongation of existing hospitalization to treat the AE
 - The following are not considered hospitalizations for the purposes of assessing seriousness:
 - Emergency room visits <24 hours;
 - Hospitalizations for preplanned procedures;
 - Hospitalization for study-related treatment and procedures.
- Results in persistent or significant disability/incapacity, where disability is defined as a substantial disruption of a person's ability to conduct normal life functions, either reported or defined as per clinical judgment.
- Is a congenital anomaly/birth defect (if exposure to product just before conception or during pregnancy resulted in an adverse outcome in the child).
- Is any other important medical event that based upon appropriate medical judgement may jeopardize the patient or may require medical or surgical intervention to prevent one of the other outcomes listed in the definitions above. (eg, may not result in death, be life-threatening, or require hospitalization). Examples of such events include allergic bronchospasm requiring intensive treatment in an emergency room or at home, and blood dyscrasias, or convulsions that do not result in inpatient hospitalization, or development of drug dependency or drug abuse.

8.2.2. Reporting of Serious Adverse Events (within 24 hours)

SAEs must be reported to the Sponsor's Pharmacovigilance group or its designee within 24 hours from the time the Investigator first becomes aware of the SAE. Comprehensive information available at the time of initial reporting (including narrative description, medical history, and concomitant medications) needs to be provided with careful consideration regarding causality and

serious criterion. The SAE reporting process and contact information are provided on the paper SAE Form Completion Guidelines.

All SAEs occurring from the time the ICF is signed through the Safety Follow-up Period (30 days after the last dose of study drug or discontinuation, whichever is earlier) must be reported to the Sponsor's Pharmacovigilance group or its designee. Any untoward medical event that occurs after the Safety Follow-up Period or discontinuation (whichever is earlier) is not considered an SAE, unless the Investigator considerers that the SAE is related to the study drug.

After the initial SAE notification to the Sponsor's Pharmacovigilance group or its designee, all follow-up SAE information will be submitted each time they become available (for example, clinical diagnosis, outcome, causality assessment, results of specific investigations) on a follow-up paper SAE form.

The Investigator also must submit further information if it is required by the Sponsor, the director of the study site, or an institutional review board (IRB)/independent ethics committee (IEC).

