3.2.4. Safety Follow-Up Period and 30-Day Safety Follow-Up Visit

The safety follow-up period is the time from the date of last dose of study therapy through the 30-day safety follow-up visit, which must be performed 30 days (±3 days) following the last dose of study therapy. If the patient starts new anticancer therapy within 30 days of the last dose of TAS-120, the 30-day safety follow-up visit should be performed before the start of new anticancer therapy. Every effort should be made to perform the assessments outlined in Table 1. If the patient is unable to return to the study site, a follow-up phone call can be made by the study site to collect any new safety information that occurred during the Safety Follow-up Period.

After the 30-day Safety Visit, only AEs that are serious and drug-related will be assessed.

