8.2.3. Reporting of Deaths

All deaths, including death due to disease progression, occurring from the time the ICF is signed through the Safety Follow-up Period (30 days after the last dose of study drug or discontinuation, whichever is earlier) must be reported as an SAE on a paper SAE form **within 24 hours** from the time the Investigator first becomes aware of the death.

Death is not an acceptable AE/SAE term; death is an outcome of an SAE. When reporting a death, site personnel will be required to identify which of the following best describes the category for cause of death:

- Toxicity caused by study drug
- Disease progression
- Clinical disease progression
- Other causes

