6.5.2.2. Adverse Events

An adverse event (AE) is any untoward medical condition that occurs in patients while participating in this clinical study. Adverse events will be coded according to the Medical Dictionary for Regulatory Activities (the most up-to-date version at the time of analysis) terminology and the severity of the toxicities will be graded according to NCI CTCAE (Version 5.0 or most up-to-date version at the time of analysis), where applicable.

A treatment-emergent AE (TEAE) is defined as an AE that is starting or worsening at the time of or after the first dose of study drug administration and within 30 days after the last dose of study drug, and do not necessarily have a causal relationship to the use of the study drug. All AEs captured in the database will be listed; however, only TEAEs will be summarized.

The following AE summary tables will be generated:

- 1) Summary of AEs with the number and percentage of patients reporting AEs, serious AEs, grade ≥ 3 AEs, AEs leading to study drug discontinuation, interruption and dose reduction, and AEs with outcome of deaths.
- 2) Summary of treatment-related AEs with the number and percentage of patients reporting AEs, serious AEs, grade ≥ 3 AEs, AEs leading to study drug discontinuation, interruption and dose reduction, and AEs with outcome of deaths.
- 3) Summary of AEs by worst CTC Grade (grade 1, 2, 3, 4, 5, any grade, Grade ≥ 3) presented by System Organ Class (SOC) and Preferred Term (PT).
- 4) Summary of treatment-related AEs by worst CTC grade (Grade 1, 2, 3, 4, 5, any grade, Grade ≥ 3) presented by SOC and PT.
- 5) Grade \geq 3 AEs by worst CTC Grade (grade 3, 4, 5, 3-5) presented by SOC and PT.
- 6) Grade ≥ 3 treatment-related AEs by worst CTC Grade (grade 3, 4, 5, 3-5) presented by SOC and PT.
- 7) Summary of AEs leading to death by SOC and PT.
- 8) Summary of the most common AEs (≥10% incidence) and median time to first AE by SOC and PT.

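### Protocol 8.2.2 ends SAE status at an undefined 'discontinuation', which on some readings conflicts with the 30-day safety window for serious events judged unrelated

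*Protocol*

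**What the plan says.** Protocol 8.2.2 makes two statements about when SAE reporting ends. The first requires that SAEs from consent "through the Safety Follow-up Period (30 days after the last dose of study drug or discontinuation, whichever is earlier) must be reported". The second reads: "Any untoward medical event that occurs after the Safety Follow-up Period or discontinuation (whichever is earlier) is not considered an SAE". It is followed at once by an exception: "unless the Investigator considerers that the SAE is related to the study drug".

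Protocol 8.2.3 applies the parenthesis of the first statement to deaths, which "through the Safety Follow-up Period (30 days after the last dose of study drug or discontinuation, whichever is earlier) must be reported as an SAE". It does not repeat the second statement.

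The other safety windows do not stop at discontinuation:

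- Protocol 3.2.4: "The safety follow-up period is the time from the date of last dose of study therapy through the 30-day safety follow-up visit". Protocol 3.2 gives the same 30 days as a minimum.
- Protocol 8.1.1: "All AEs will be collected from the time the main ICF is signed through 30 days after the last dose of study therapy", or to the start of new antitumor therapy if that is sooner. Related SAEs continue to be collected during survival follow-up. The Schedule of Events is similar.
- SAP 6.5.2.2 counts as treatment-emergent an event that starts or worsens from the first dose and "within 30 days after the last dose of study drug". SAP 5.1 (Table 2) and SAP 8.2 use the same period.

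The protocol has one section on discontinuing treatment (4.4) and another on discontinuing the study (4.5). Sections 8.2.2 and 8.2.3 point to neither.

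**The concern.** Sites will look to 8.2.2 and 8.2.3 for what must reach Pharmacovigilance within 24 hours. If a site takes discontinuation to mean stopping drug, the second statement of 8.2.2 closes the SAE window when the safety follow-up period begins, or during it. An unrelated hospitalisation on day 10 after the last dose would then be an AE under 8.1.1 and meet a seriousness criterion in 8.2.1, yet not count as an SAE under 8.2.2.

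Two things are at stake. The Sponsor would lose prompt sight of serious events that only the Investigator has judged unrelated, in a study with no control arm and, in Cohort 4, a combination not previously assessed in patients. And the SAE tables in SAP 6.5.2.5, built on a 30-day period, could be filled differently by sites that read the clause differently.

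**Working it through.** The plan gives no figure to reproduce. The check sets the windows side by side and counts days under each reading.

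| Source | Governs | Window ends |
|---|---|---|
| Protocol 3.2 | Safety assessment | At least 30 days after last day of therapy |
| Protocol 3.2.4 | Safety follow-up | 30-day visit (±3 days) |
| Protocol 8.1.1, Schedule of Events | AE collection | Day 30, or new anticancer therapy |
| Protocol 8.2.2, first statement | SAE reporting | Ambiguous parenthesis |
| Protocol 8.2.2, second statement | SAE status of unrelated events | Earlier of the end of safety follow-up and discontinuation |
| Protocol 8.2.3 | Deaths reported as SAEs | Ambiguous parenthesis |
| SAP 5.1, 6.5.2.2, 8.2 | Safety summaries | Day 30 |

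Let day 0 be the last dose and *d* the days from then to the date of discontinuation. If the window closes at discontinuation, shortfall = max(0, 30 − *d*).

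1. **Thirty days after whichever date is earlier.** If discontinuation falls on or after the last dose, the earlier date is the last dose. The window is 30 days and the shortfall is 30 − 30 = 0. This reading is open for the parenthesis in 8.2.2 and 8.2.3. It does not fit the second statement of 8.2.2, where discontinuation is an end point alongside the Safety Follow-up Period.
2. **Treatment discontinuation (4.4).**
   - Dated on the last dose day, *d* = 0: shortfall 30 days.
   - After the full 28-day recovery limit of 5.3.1.1, *d* = 28: shortfall 30 − 28 = 2 days.
   - Under the delay rule in 4.4, which counts more than 28 days from the scheduled start of the next cycle, take a last dose on Day 14 of a 28-day cycle as an example. The next cycle is due 29 − 14 = 15 days later, so *d* exceeds 15 + 28 = 43 and the shortfall is 0.
3. **Study discontinuation as in 4.5** (death, loss to follow-up, withdrawal of consent to follow-up). No further data could be collected anyway, so there is no real conflict.
4. **Study discontinuation as the protocol uses it elsewhere.** Section 5.3.1.1 removes a patient with unrecovered toxicity permanently from the study, citing 4.4 (*d* = 28, shortfall 2). Table 7 does the same for a confirmed mean QTcF above 500 ms, with re-evaluation due within 7 days of the first abnormal ECG. If the last dose was on the day of that ECG (my assumption) and discontinuation is dated at that re-evaluation, *d* is at most 7 and the shortfall at least 30 − 7 = 23 days. Section 7.2.1.1.1 describes patients discontinued from the study before progression who are still in a follow-up period. The study reading is therefore not confined to 4.5.

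What falls in the gap under readings 2 and 4:

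- Related SAEs: nothing, because of the exception in 8.2.2 and the continued collection in 8.1.1.
- Unrelated serious events: still collected as AEs to day 30 (or new therapy), but without SAE status or 24-hour reporting.
- Deaths: captured by survival follow-up (3.2.6) and listed for every period by SAP 6.5.2.1. Survival contact is every 12 weeks (±2 weeks), so it does not replace 24-hour reporting.

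**The case against.** The best defence is that this is ambiguity and not contradiction. Both 8.2.2 and 8.2.3 tie reporting to the named Safety Follow-up Period, which 3.2.4 runs to the 30-day visit. Readings 1 and 3 lose nothing. Section 3.2.4 restricts collection to related serious events only after the 30-day visit, and the Schedule of Events only after day 30 or new anticancer therapy. This stands for the parenthesis, so 8.2.3 alone does not show that death reporting stops at discontinuation. It does not rescue the second statement of 8.2.2, and reading 4 shows that the study meaning is not harmless either.

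A reader might infer three stronger things that the documents do not support:

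- *That SAEs and deaths in the month after stopping are lost to the trial.* Related SAEs are excepted, unrelated events remain AEs, and deaths have two other routes of capture.
- *That discontinuation always precedes day 30, so the window always vanishes.* The delay rule in 4.4 can place it later, and after a 28-day hold the shortfall is 2 days.
- *That 168 × 30 = 5,040 patient-days (5,040 / 365.25 = 13.8 patient-years) are affected.* This is an upper bound under reading 2. It needs the full 55 + 55 + 24 + 34 = 168 patients, every site on that reading, *d* = 0 for all, and every patient alive without new anticancer therapy for 30 days. No number of affected events follows from it.

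**Conclusion.** The concern holds as an inconsistency in safety reporting. The second statement of 8.2.2 uses an undefined term as a cut-off. If the term means treatment discontinuation, or the toxicity-driven removal from study in 5.3.1.1 and Table 7, the statement conflicts with every other safety window in the protocol and SAP.

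The exposure is limited to serious events judged unrelated, over a period of at most about 30 days per patient and sometimes none. For deaths, only 24-hour reporting as an SAE is at risk, and only if the ambiguous parenthesis is read as a cut-off.

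The effect on the SAP's SAE tables assumes that the seriousness recorded for such events follows 8.2.2, which the documents do not state. No efficacy endpoint, sample size or futility rule is affected.

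**What to change.** - In 8.2.2 and 8.2.3, delete the discontinuation alternative from the parenthesis ("30 days after the last dose of study drug or discontinuation, whichever is earlier") and from the second statement of 8.2.2. Alternatively, define discontinuation there as the events in 4.5 only: death, loss to follow-up, or withdrawal of consent to all follow-up.
- State that all SAEs and deaths, regardless of causality, are reportable from ICF signature to day 30 after the last dose of study therapy, and that related SAEs remain reportable afterwards.
- Reconcile both sections with 3.2, 3.2.4, 8.1.1, the Schedule of Events and the SAP's on-treatment and TEAE definitions.
- Say explicitly whether the new-antitumor-therapy cut-off applies to SAEs and deaths. It appears in 8.1.1 and the Schedule of Events but not in 8.2.2, 8.2.3 or the SAP window. Simply aligning 8.2.2 with day 30 would leave a fresh mismatch with 8.1.1.

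The cost is wording in two protocol sections, a matching line in the SAE form guideline, and possibly a few more SAE reports. The 30-day visit already exists, so no new visit is needed.
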